#### **Pregnancy Testing**

A highly sensitive serum pregnancy test should be completed at screening and within 7 days of initiation of investigational product for females of childbearing potential.

Note: Females who have undergone a bilateral tubal ligation/occlusion should have pregnancy testing per protocol requirements. (If a female subject, or the partner of a

male subject, becomes pregnant it must be reported on the Pregnancy Notification Form, see [Figure 11-2](#)). Refer to Section [11.5](#) for contraceptive requirements.

Additional pregnancy testing should be performed at monthly intervals during treatment with protocol-required therapies and at the 30 day and 140 day follow-up visit

Additional on-treatment pregnancy testing may be performed at the investigator's discretion or as required per local laws and regulations.

#### **8.2.6 Pharmacokinetic Assessments**

All subjects enrolled will have pharmacokinetic samples assessed.

Blood samples of approximately 5 and 3 mL will be collected for measurement of serum concentrations of AMG 994 and AMG 404, respectively as specified in the Schedule of Activities (Section [1.3](#)). Instructions for the collection and handling of biological samples will be provided by the sponsor. The actual date and time (24-hour clock time) of each sample will be recorded.

#### **8.2.7 Pharmacodynamic Assessments**

Biopsy tissue will be collected for evaluation of pharmacodynamic changes as specified in the Schedule of Activities (Section [1.3](#)).

#### **8.2.8 Pharmacogenetic Assessments**

If the subject consents to the optional pharmacogenetic portion of this study, DNA analyses may be performed. These optional pharmacogenetic analyses focus on inherited genetic variations to evaluate their possible correlation to the disease and/or responsiveness to the therapies used in this study. The goals of the optional studies include the use of genetic markers to help in the investigation of advanced solid tumors and/or to identify subjects who may have positive or negative response to AMG 994 and AMG 404 combination therapy. No additional samples are collected for this part of the study. For subjects who consent to this/these analysis/analyses, DNA may be extracted.

The final disposition of samples will be described in Section [11.6](#).

**Product:** AMG 994 and AMG 404

**Protocol Number:** 20190136

**Date:** 16 June 2022

---

Page 111 of 180

**Product:** AMG 994 and AMG 404

**Protocol Number:** 20190136

**Date:** 16 June 2022

Page 112 of 180

## **9. Statistical Considerations**

### **9.1 Statistical Hypotheses**

This is a phase 1 study and no formal statistical hypotheses will be tested.

### **9.2 Sample Size Determination**

It is anticipated that approximately 214 subjects will be enrolled in this study.

Approximately 94 subjects will be enrolled in the dose-exploration cohorts (Part 1). Up to 120 subjects will be enrolled in the dose-expansion cohorts (Part 2), 30 subjects in each of 4 tumor types (mesothelioma, NSCLC squamous cell carcinoma and adenocarcinoma [if upon screening found to be MSLN positive], pancreatic adenocarcinoma, and high grade serous ovarian carcinoma).

The sample size in the dose-escalation phase is based on practical consideration and is consistent with conventional oncology studies with the objective to estimate the MTD/MTCD. With 3 subjects in a cohort, there is a 27% to 70% probability of observing at least 1 DLT if the true DLT rate is 10% to 33% and with 6 subjects in a cohort, there is a 47% to 91% probability.

In the dose-expansion cohorts, a total subject sample size of 120 will provide a 91% probability of observing at least 1 adverse event with 2% incidence rate. An exact 95% binomial CI will be provided for overall response rate. With the 30 subjects in a cohort of subjects with a particular tumor type and a 20% overall response rate, the expected 95% CI would be 8% to 39%. Under certain circumstances, the sample size dose expansion will be smaller due to early stopping; see Section [9.4.1.1](#) for details.

### **9.3 Analysis Sets, [REDACTED] and Covariates**

#### **9.3.1 Analysis Sets**

The analysis of all endpoints, unless noted otherwise, will be conducted on the Safety Analysis Set defined as all subjects that are enrolled and receive at least 1 dose of AMG 994 or AMG 404.

[figure not shown]
The analysis of DLT in the initial safety review period [REDACTED] will be conducted on the Early DLT Analysis set defined as all subjects that are enrolled and receive at least 1 dose of AMG 994 with an evaluable early DLT endpoint (evaluable in AMG 994 monotherapy cohort per [Table 6-2](#)).

The analysis of DLT in the cumulative safety review period will be conducted on the Cumulative DLT Analysis set defined as all subjects that are enrolled and receive at least 1 dose of AMG 994 or AMG 404 with an evaluable cumulative DLT endpoint (experience a DLT during monotherapy cohort or evaluable in combination therapy cohort per [Table 6-2](#)).

The analysis of objective response will be conducted on the Efficacy Evaluable Analysis set defined as all subjects that are enrolled to a dose expansion cohort and receive at least 1 dose of AMG 994 or AMG 404 with at least 1 tumor lesion that is measurable in contrast-enhanced CT as defined by modified RECIST 1.1, with the following exceptions. The following subjects will be excluded from the Efficacy Evaluable Analysis set: 1) subjects who are lost to follow-up and have no on study radiological assessments and 2) subjects who have been on study less than 8 weeks and have no on study radiological assessments.

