### 3. Objectives and Endpoints

Objectives	Endpoints
Primary	

 
To evaluate the safety, tolerability, and maximum tolerated dose (MTD)/maximum tolerated combination dose (MTCD) or recommended phase 2 dose (RP2D) of AMG 994 as monotherapy and AMG 994 in combination with AMG 404 in subjects with advanced solid tumors
 
	
 
Dose-limiting toxicities (DLTs)
 
Treatment-emergent and treatment related adverse events (including all adverse events, grade <math>\geq 3</math>, serious adverse events, fatal adverse events, adverse events requiring permanent discontinuation of study treatment, and immune-related events)
 
Changes in vital signs, electrocardiograms (ECGs), and clinical laboratory tests
 

Secondary	

 
Preliminary evaluation of anti-tumor activity of AMG 994 as monotherapy and AMG 994 in combination with AMG 404
 
	
 
Objective response (OR) per modified Response Evaluation Criteria in Solid Tumors (RECIST) 1.1
 
Duration of response (per modified RECIST 1.1)
 

	
 
Overall survival (OS)
 
Progression-free survival (per modified RECIST 1.1)
 
Time to progression (per modified RECIST 1.1)
 
Time to subsequent therapy
 

 
Characterize the PK of AMG 994 monotherapy and AMG 994 in combination with AMG 404
 
	
PK parameters
 
 
Maximum serum concentration (<math>C_{max}</math>)
 
Minimum serum concentration (<math>C_{min}</math>)
 
Area under the concentration-time curve (AUC) over the dosing interval
 
Half-life (<math>t_{1/2}</math>), if feasible
 

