**Table 4-1: MSLN Expression in Solid Tumors**

Tumor Type	Patients with MSLN Expression – Positive Disease (%)
Mesothelioma	82
Epithelioid	95
Sarcomatoid	0
Pancreatic adenocarcinoma	85
Epithelial ovarian cancer	70
High-grade serous	75
Endometrioid	69
Mucinous	11
Clear cell	52
NSCLC	57
Adenocarcinoma	64
Squamous	21
SCLC	0
Esophageal cancer	28
Gastric cancer	47
Biliary cancer	
Extrahepatic	95
Intrahepatic	10
Other or unspecified	42
Colorectal cancer	30
Cervical cancer	25
Endometrial cancer	59
Breast cancer	
Triple negative	66
Other	1.6
Unspecified	9

MSLN = mesothelin, NSCLC = nonsmall-cell lung cancer

Study assessments will include measures of safety, tolerability, PK, and pharmacodynamics, immunogenicity, and preliminary anti-tumor activity.

AMG 994 will be administered by [REDACTED] cycle

(on days [REDACTED]) and AMG 404 will be administered by

[REDACTED] cycle. The study will be

conducted in 2 parts: Part 1 – Dose Exploration and Part 2 – Dose Expansion. Part 1 is aimed at evaluating the safety, tolerability, PK, and pharmacodynamics of AMG 994 and AMG 404 combination using sequential and concurrent initiation of dosing: (a) 1 cycle of AMG 994 monotherapy followed by combination of AMG 994 and AMG 404 from cycle 2 onwards and (b) AMG 994 and AMG 404 dosing starting on cycle 1 day 1. The MTD/MTCD of the combination in subjects with locally advanced or metastatic solid tumors will be determined using a Bayesian Logistics Regression Model (BLRM) design. Part 2 will further evaluate the safety of the MTD/MTCD and/or a biologically active dose (eg, recommended phase 2 dose [RP2D]) of the combination in specific tumor types.

[figure not shown]
The dose expansion part of the study (Part 2) will be opened once the MTD/MTCD/RP2D of the combination has been determined in Part 1.

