## Part 2 – Dose Expansion

Upon completing the dose exploration phase of the study, and depending on data obtained, dose expansion may proceed in subjects with certain advanced solid tumors of types known to express MSLN:

- Mesothelioma
- NSCLC squamous cell carcinoma and adenocarcinoma, if upon screening found to be MSLN positive
- Pancreatic adenocarcinoma
- High grade ovarian carcinoma (platinum resistant)

AMG 994 plus AMG 404 combination will be administered from cycle 1, day 1.

The overall study design is described by a study schema in Section 1.2. The endpoints are defined in Section 3.

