## Methods of Measurement

- **Measurement of Lesions** - The longest diameter of selected lesions should be measured in the plane in which the images were acquired (axial plane). All measurements should be taken and recorded in metric notation. All baseline evaluations should be performed as closely as possible to the beginning of treatment and not more than 4 weeks before study Day 1.
- **Methods of Assessment** - The same method of assessment and the same technique should be used to characterize each identified and reported lesion throughout the trial.
- **CT/MRI** – Contrast-enhanced CT or MRI should be used to assess all lesions. Optimal visualization and measurement of metastasis in solid tumors requires consistent administration (dose and rate) of IV contrast as well as timing of scanning. CT and MRI should be performed with  $\leq$  5 mm thick contiguous slices.

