9.5.2 Analyses of Secondary Efficacy Endpoint(s)

Listings of secondary efficacy endpoints will be produced for all subjects in the dose-escalation cohorts and the dose-expansion cohorts.

For all subjects in the Efficacy Analysis Set, the proportion of subjects and 95% CL with an objective response (complete or partial response per modified RECIST 1.1) will be tabulated by tumor type and planned dose level and schedule.

For all subjects in the Efficacy Analysis Set, Kaplan-Meier methods will be used to estimate the time of event curve, median time to event, and percentiles with 95% CI for

1) Duration of response (DOR, per modified RECIST 1.1),

2) Overall survival (OS)

3) Progression-free survival (PFS, per modified RECIST 1.1)

4) Time to progression (TTP, per modified RECIST 1.1) and

5) Time to subsequent therapy.

Kaplan-Meier methods will be used to estimate appropriate landmarks for DOR, OS, PFS and TTP (eg, 1-year PFS)

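### The efficacy set admits only dose-expansion subjects with a CT-measurable lesion, so monotherapy activity gets no summary estimate and subjects measurable only on MRI drop out of the response table

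*Protocol*

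**What the plan says.** **Objective.** Protocol Section 3 (repeated in SAP 2.1) lists as secondary the "Preliminary evaluation of anti-tumor activity of AMG 994 as monotherapy" and, in the same line, of the combination.

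**Analysis set.** Protocol 9.3.1 assigns objective response to the Efficacy Evaluable set: "all subjects that are enrolled to a dose expansion cohort and receive at least 1 dose of AMG 994 or AMG 404", and "with at least 1 tumor lesion that is measurable in contrast-enhanced CT as defined by modified RECIST 1.1". SAP 6.1 repeats this. The default for other endpoints is the Safety Analysis Set, unless something else is noted.

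**Treatment.** In Part 2, "AMG 994 plus AMG 404 combination will be administered from cycle 1, day 1". Protocol 4.1 places the monotherapy period in Part 1, under sequential initiation: "1 cycle of AMG 994 monotherapy followed by combination of AMG 994 and AMG 404 from cycle 2 onwards".

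**Planned output.** Under Protocol 9.4.2.2 and SAP 9.5.2, objective response "will be tabulated by tumor type and planned dose level and schedule", and five time-to-event endpoints get Kaplan-Meier summaries. All six are assigned to an Efficacy Analysis Set. The same sections plan listings of the secondary efficacy endpoints for subjects in both parts.

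**Imaging.** Appendix 11 of the protocol says "Contrast-enhanced CT or MRI should be used to assess all lesions" and defines measurable lesions on either modality. Section 8.2.2 also allows both. Inclusion criterion 106 sets no modality limit.

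**The concern.** Three parts of the plan do not fit together.

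1. The objective asks about monotherapy, but the set that feeds the response estimate contains no cohort planned to receive it.
2. The response table is broken down by dose level and schedule, but the escalation dose levels are in the part of the study that the set leaves out.
3. The set cites modified RECIST 1.1 for measurability and then narrows it to CT, which the cited criteria do not do.

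At stake are a stated objective reported only through listings, a response table that may disagree with the futility count in the same tumor type, and uncertainty about which subjects enter the time-to-event summaries.

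**Working it through.** **The plan's own figures first.** With 6 responders in 30 (20%), the exact interval is

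- lower = Beta quantile(0.025; 6, 25) = 7.7%
- upper = Beta quantile(0.975; 7, 24) = 38.6%

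This matches the stated 8% to 39%. The futility rule stops on 0 responders in 10, or at most 1 in 20, so P(stop) = q^10 + 10·p·q^9·q^10, with q = 1 − p.

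- p = 0.05: 0.5987 + 0.3151 × 0.5987 = 0.787 (stated 78.7%)
- p = 0.20: 0.1074 + 0.2684 × 0.1074 = 0.136, so 86.4% continue (stated 86.4%)

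None of these figures is in dispute. The point concerns who is in the set.

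**Who is in the set.** Section 9.2 gives about 94 subjects in Part 1 and up to 120 in Part 2, together 214.

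- Part 1: 0 of 94 are in the Efficacy Evaluable set. 94/214 = 43.9% of planned enrollment.
- Part 2: at most 120/214 = 56.1%, all started on the combination.

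No planned monotherapy period contributes to the response rate. The dose-level rows reduce to whatever Part 2 carries forward, which Protocol 4.1 describes as the MTD/MTCD and/or a biologically active dose.

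**CT against MRI.** Take a Part 2 subject whose only measurable disease is seen on MRI.

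| Rule | Subject counted? |
|---|---|
| Inclusion 106 | Yes, no modality limit |
| Appendix 11 measurability | Yes, CT or MRI |
| Futility (Protocol 9.4.1.1) | Yes: treated subjects, response per modified RECIST 1.1 |
| Response table (Protocol 9.3.1, SAP 6.1) | No, CT required |

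Such a subject could be a responder for futility and be absent from both numerator and denominator of the response rate. The documents do not say how many there would be. As an assumption, suppose 5%, 10% or 20% of each group of 30 have no CT-measurable lesion:

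| Share | Subjects left of 30 | Example near 20% response | Exact 95% interval |
|---|---|---|---|
| 0% | 30 | 6/30 | 8% to 39% |
| 5% | 28.5 | not calculated | not calculated |
| 10% | 27 | 5/27 | 6% to 38% |
| 20% | 24 | 5/24 | 7% to 42% |

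The loss of precision is small. The mismatch between the two counts is the larger matter.

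**What a Part 1 table could show.** Protocol 4.1 gives 3 to 6 subjects per cohort for Part 1a. With no responders the upper exact limit is 1 − 0.025^(1/n): 71% for 0/3 and 46% for 0/6.

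**Set name.** Section 9.3.1 and SAP 6.1 define an Efficacy Evaluable Analysis set and assign it to objective response. Protocol 9.4.2.2 and SAP 9.5.2 use an Efficacy Analysis Set for six endpoints. If the two are the same, Part 1 is outside all six. If not, the population for those analyses is undefined.

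**The case against.** The study tests no hypothesis and calls its activity objective preliminary. Part 1 cohorts are small, and individual listings for them are a defensible choice. One monotherapy cycle can yield little confirmed response, since confirmation needs a repeat scan at least 4 weeks later. The timing of the cycle 1 scan is redacted, so it cannot be verified that a scan precedes the first AMG 404 dose. All of this stands. It limits what the fix can deliver, but it does not supply a summary for the stated objective or remove the CT conflict.

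A reader might also infer more than the documents support:

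- *That Part 1 efficacy has no data.* It is collected and listed per subject; only a summary is missing.
- *That the dose-level table is empty.* It keeps the Part 2 dose or doses and lacks the escalation levels.
- *That every subject followed by MRI is dropped.* Only those with no CT-measurable lesion are.
- *That the recommended dose would be chosen without this table because of the set definition.* Part 2 opens only after that dose is determined, and the table comes at the primary or final analysis, so it could not inform the choice.
- *That no subject in the set ever receives AMG 994 alone.* Section 6.2.2.2 lets a subject continue on it after AMG 404 is withheld or stopped, although this is not clean evidence on monotherapy.
- *That 43.9% of subjects are excluded from every efficacy estimate.* This is certain only for objective response. For the time-to-event endpoints it depends on what the undefined set name means.

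**Conclusion.** The point holds in this form. Monotherapy activity is a stated secondary objective with no planned summary estimate. Part 1, about 94 of 214 subjects, is outside the response rate, so the breakdown by dose level covers only the Part 2 dose or doses. The 43.9% is a share of enrollment, not a measure of bias or lost precision. The CT-only condition contradicts the criteria it cites and can make the response table disagree with the futility count; the number affected is unknown and probably small. The set named for objective response and the five time-to-event endpoints is not defined under that name. SAP Section 10 reports no changes from the protocol's analyses, so nothing there resolves these points. The conclusion rests on the visible text; the descriptions of Parts 1b and 1c and the scan timing are not available.

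**What to change.** 1. In Protocol 9.3.1 and SAP 6.1, change the lesion condition to measurable by contrast-enhanced CT or MRI under modified RECIST 1.1.
2. Use one name for the efficacy set throughout, and state it for objective response and for each time-to-event endpoint. Add a descriptive Part 1 table of response by dose level and schedule, as n/N with an exact interval. Leave the Part 2 analysis by tumor type unchanged.
3. For monotherapy, report unconfirmed response and change in the target-lesion sum at the last scan before the first AMG 404 dose, where such a scan exists. Otherwise remove monotherapy from the efficacy objective.

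The cost is wording in both documents and a few tables. Part 1 intervals will be very wide (0 to 71% for 0/3, 0 to 46% for 0/6) and should be labelled descriptive. Sample size, futility rule and stated operating figures do not change.

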#### **9.3.2 Covariates**

The relationship of covariates to efficacy endpoints will be explored as appropriate.

#### **9.3.4 Handling of Missing and Incomplete Data**

The handling of missing and incomplete data is described in the statistical analysis plan.

## 9.4 Statistical Analyses

The statistical analysis plan will be developed and finalized before database lock. Below is a summary of the timing and methods for the planned statistical analyses. To preserve study integrity, the final analysis will be conducted and reported following the end of study, as defined in Section 4.4.1.

### 9.4.1 Planned Analyses

#### 9.4.1.1 Interim Analysis and Early Stopping Guidelines

Safety data will be reviewed on an ongoing basis. Based on accumulating safety data, BLRM will be used to make dosing recommendations. In DLRMs, Amgen, in consultation with the site investigators, will review the BLRM recommended dose level and will review all available cumulative data by cohort prior to making dose escalation recommendations. As a sensitivity analysis, a 1-parameter Continual Reassessment Method model may be used to estimate the dose-toxicity relationship and in particular to estimate the dose level with a 25% DLT rate in order to help make dose escalation decisions. Adverse events, including late onset immune-mediated toxicities, and DLTs observed in all subjects will be evaluated continually and fully integrated into all DLRMs and considered in all enrollment and dosing decisions. If during the study there is any grade 5 adverse event (or any 2 of the same grade 4 adverse events) at least possibly related to AMG 994 or AMG 404, further accrual will be suspended; Amgen will conduct a safety analysis and submit to the regulatory authority for review prior to resuming enrollment.

Given that a fixed-dose administration of AMG 404 [REDACTED] is used as part of the AMG 994 plus AMG 404 combination, the 2-parameter BLRM for single agent AMG 994 will be used. Key details of the BLRM model as used in this study are as follows. A bi-variate normal prior distribution (parameters "a" and "b") is used for the BLRM model with bi-variate normal prior are as follows: the mean natural log (ln) of "a"  $\ln(a) = [REDACTED]$ , SD of "a"  $SD(\ln(a)) = [REDACTED]$ , mean  $\ln(b) = [REDACTED]$ ,  $SD(\ln(b)) = [REDACTED]$  and correlation = [REDACTED]. The target toxicity probability interval (TPI) is defined as a rate at least [REDACTED] and less than [REDACTED]; an excessive or unacceptable TPI is a rate of [REDACTED] or higher. The prior distribution is specified such that probability of DLT is [REDACTED] for the starting dose [REDACTED] and [REDACTED] for the reference dose [REDACTED] where the probability that the true DLT rate is [REDACTED] at the lowest planned dose is [REDACTED] and the probability the true DLT rate is [REDACTED] at the reference dose is [REDACTED]. The BLRM will be used [REDACTED] to recommend the next dose level and at the end of dose [REDACTED]

exploration the recommended MTD will be the level with the highest probability of the target TPI, but with a less than █ probability of an excessive or unacceptable TPI.

During dose expansion, if the observed rate of responses in a particular tumor type is less than 10% after  $n = 10$  and  $n = 20$  subjects in that tumor type, then enrollment to that tumor type will be terminated due to futility. For purposes of assessing futility, a response is defined as an objective response per modified RECIST 1.1. The guidelines for early termination of enrollment for a tumor type due to futility are as follows:

Number of Treated Subjects in a Tumor Type	Enrollment Stopping Rule
10	0 responders
20	1 or fewer responders
30	Enrollment complete

If the true response rate is 5% then these termination guidelines result in a 78.7% probability of terminating tumor type enrollment at or prior to  $n = 20$  subjects. If the true response rate is 20% then there is an 86.4% probability of continuing enrollment past  $n = 20$  subjects.

During dose expansion, Amgen will conduct evaluations of the ongoing grade 4 or higher treatment-related adverse event rate to assess if the threshold for possible early trial termination has been reached. If this threshold is met, enrollment to dose expansion will be halted pending review of safety data by the DLRT. After receiving the DLRT recommendation, Amgen will choose to take 1 of the following actions.

- Terminate the trial
- Amend the protocol to potentially improve the benefit/risk for subjects (eg, increase safety monitoring, modify dose/schedule, mandate premedication)
- Continue dose expansion without any changes

The stopping rules use a Bayesian approach proposed by Thall, Simon, and Estey (1995) to terminate the study if the posterior probability that the grade 4 or higher treatment-related adverse event rate is greater than 20% is  $> 80\%$ . The stopping boundaries assume a prior distribution of Beta (0.40, 1.60) are presented in [Table 9-1](#) and the operating characteristics with pre-specified batch size of 10 new subjects per batch are presented in [Table 9-2](#). The operating characteristics in [Table 9-2](#) provide the probability of stopping the trial early for given hypothetical true rate of grade 4 or higher treatment-related adverse events, whereas the stopping criteria in [Table 9-1](#) are based

on situations where the empirical evidence would result in the posterior probability of  $\geq 80\%$  that the true grade 4 or higher treatment-related adverse event rate is  $\geq 20\%$ .

**Table 9-1. Stopping Boundary for Dose Expansion With Posterior Probability of 80% and Grade 4 or Higher Treatment-Related Adverse Event Limit of 20%**

Number of subjects	Hold enrollment if observing this many grade 4 or higher treatment adverse events
20	$\geq 6$
40	$\geq 11$
60	$\geq 15$
80	$\geq 20$
100	$\geq 24$
120	Dose Expansion Complete

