**Table 9-2. Operating Characteristics With Batch Size of 20 Subjects**

True grade 4 or higher treatment-related adverse event rate	Probability of early stopping of dose expansion	Average dose expansion sample size
0.10	1.2%	118.8
0.15	9.6%	111.5
0.20	37.6%	90.1
0.25	76.0%	59.9
0.30	95.7%	38.0

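### The text gives batches of 10 for the dose-expansion safety stopping rule but both tables use batches of 20, and the boundary column counts events where the rule needs subjects.

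*Protocol*

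**What the plan says.** Protocol 9.4.1.1 defines an enrollment hold for dose expansion. It applies when the posterior probability that the rate of grade 4 or higher treatment-related adverse events exceeds 20% is above 80%, under a Beta(0.40, 1.60) prior. The text says that Table 9-2 gives the "operating characteristics with pre-specified batch size of 10 new subjects per batch".

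The two tables say something else:

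- Table 9-1 gives hold boundaries only at 20, 40, 60, 80 and 100 subjects: 6, 11, 15, 20 and 24. Expansion is complete at 120.
- Table 9-2 is titled "Operating Characteristics With Batch Size of 20 Subjects".

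The column of hold counts in Table 9-1 is headed "Hold enrollment if observing this many grade 4 or higher treatment adverse events".

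SAP 7.1 repeats the sentence with 10, and its Tables 7.1.1 and 7.1.2 repeat the titles, headings and values. SAP section 10 declares no changes from the protocol, so the SAP does not settle the matter.

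Once the boundary is met, enrollment is held for review by the dose level review team. The sponsor may then terminate, amend, or "Continue dose expansion without any changes".

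**The concern.** A pre-specified safety rule needs one look schedule and one counting unit, because its operating characteristics hold only for that combination. Here the schedule in the text differs from the one in the tables. The figure of 10 cannot safely be dismissed as a misprint: it is labelled pre-specified, the posterior rule can be evaluated at any number of subjects, and the futility rule in the same section does look at 10 subjects per tumor type.

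The heading raises a second question. A Beta prior updated by a count out of n subjects needs one yes/no outcome per subject. A subject with two grade 4 related events adds one under that rule but two under the printed heading. The heading also drops the word related, but the table title and the text supply it, so the open point is the unit.

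At stake is whether the people running the hold know when to look and what to count, and whether the stated stopping probabilities describe the rule they apply.

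**Working it through.** **Inputs** (protocol 9.4.1.1, Tables 9-1 and 9-2): prior Beta(0.40, 1.60); rate limit 20%; posterior threshold 80%; maximum 120 subjects; true rates 10%, 15%, 20%, 25% and 30%.

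**Step 1, boundaries.** With x affected subjects out of n, the posterior is Beta(0.40 + x, 1.60 + n − x). The boundary is the smallest x with P(rate > 0.20) > 0.80.

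| n | Boundary x | Posterior probability at x | At x − 1 |
|---|---|---|---|
| 20 | 6 | 0.826 | 0.666 |
| 40 | 11 | 0.854 | 0.754 |
| 60 | 15 | 0.809 | 0.714 |
| 80 | 20 | 0.848 | 0.777 |
| 100 | 24 | 0.823 | 0.753 |

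These equal Table 9-1. The text states the threshold once as strictly above 80% and once as at least 80%. That makes no difference to any boundary.

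The same formula at the sizes that a batch of 10 would add gives 4 at n = 10, 9 at 30, 13 at 50, 18 at 70, 22 at 90 and 26 at 110. None of these is printed.

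**Step 2, operating characteristics.** The number of affected subjects is carried forward exactly from look to look. Each batch adds a binomial count, probability at or above the boundary is removed as stopped, and the rest continues. Average N is the sum of n × P(stop at n), plus 120 × P(never stopped).

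Probability of a hold, with average N after the slash:

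| True rate | Table 9-2 | Looks every 20 | Looks every 10, from n = 10 | Looks every 10, from n = 20 |
|---|---|---|---|---|
| 10% | 1.2% / 118.8 | 1.22% / 118.80 | 2.14% / 117.76 | 1.28% / 118.75 |
| 15% | 9.6% / 111.5 | 9.59% / 111.45 | 12.50% / 108.14 | 10.44% / 110.78 |
| 20% | 37.6% / 90.1 | 37.62% / 90.07 | 43.13% / 83.94 | 41.09% / 87.72 |
| 25% | 76.0% / 59.9 | 76.02% / 59.87 | 80.87% / 52.50 | 80.07% / 56.56 |
| 30% | 95.7% / 38.0 | 95.68% / 37.95 | 97.24% / 30.92 | 97.12% / 35.39 |

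Looks every 20 match all ten entries of Table 9-2 after rounding. Neither version of looks every 10 does.

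- From n = 10, the largest gap in hold probability is 43.13 − 37.62 = 5.5 points. Average N falls by between 118.80 − 117.76 = 1.0 and 59.87 − 52.50 = 7.4.
- From n = 20, the largest gap is 80.07 − 76.02, about 4.1 points.
- The n = 10 look alone, with a hold at 4 or more of 10, would fire with probability 1.3%, 5.0%, 12.1%, 22.4% and 35.0% at the five rates.

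**Step 3, counting unit.** The match in Step 2 uses one yes/no outcome per subject, so that is the basis of Table 9-2. The documents do not say how many qualifying events an affected subject would have. As an illustration only, assume 1 + Poisson(mean − 1) events per affected subject and count events against the printed boundaries, with looks every 20:

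| Assumed mean events per affected subject | Hold probability, 10% of subjects affected | Hold probability, 15% of subjects affected |
|---|---|---|
| 1.0 (same as counting subjects) | 1.2% | 9.6% |
| 1.1 | 3.6% | 19.5% |
| 1.25 | 8.9% | 36.1% |
| 1.5 | 21.6% | 61.1% |

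**The case against.** The conflict between 10 and 20 cannot be disputed, but there is a fair case that it matters little. Table 9-1 is the working rule, and staff using it could not look at 10, 30 or 50 because no boundary is printed there. Both misreadings err on the cautious side, and a hold leads only to a review after which expansion may continue unchanged. Accrual is also suspended separately for any grade 5 event, or "any 2 of the same grade 4 adverse events", at least possibly related to either product. That trigger can act well before 6 of 20 subjects are affected. No formal hypothesis is tested, so no error rate depends on Table 9-2.

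On the unit, a 20% limit on a rate set against a number-of-subjects column points to a proportion of subjects. Protocol 9.4.2.3.2 and SAP 9.6.2 also summarise adverse events by subject incidence.

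Most of this stands, and it limits the severity. It does not remove either point. The posterior rule in the text can be applied at any n, so a wrong schedule labelled pre-specified still misleads. The subject-incidence sections govern reporting tables. They show what was probably intended, but they do not correct the heading of the hold rule.

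**Conclusion.** The concern holds on both counts, in both documents.

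The boundary and operating-characteristic tables are correct and agree with each other. The sentence introducing them does not match. If looks every 10 were really intended, the stated stopping probabilities would be too low by up to 5.5 points and the average sample sizes too high by 1.0 to 7.4 subjects. These figures rest only on the documents' own prior, threshold and maximum size, with one yes/no outcome per subject.

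The boundary column names the wrong unit for a beta-binomial rule. The size of that effect depends on an assumed number of events per affected subject, so the Step 3 figures show direction and sensitivity and are not estimates for this trial.

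This should be fixed. The practical effect is limited, because both errors would bring the hold forward or make it more frequent, and a hold triggers a review.

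**What to change.** Make the batch size agree in protocol 9.4.1.1 and SAP 7.1, in one of two ways:

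- **If 20 is intended**, change 10 to 20 in the sentence. No table value changes.
- **If 10 is intended**, add the six missing boundaries to Tables 9-1 and 7.1.1 (10: ≥4; 30: ≥9; 50: ≥13; 70: ≥18; 90: ≥22; 110: ≥26). Retitle Tables 9-2 and 7.1.2 and replace their values with those for looks every 10 from n = 10.

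In either case, retitle the boundary column in Tables 9-1 and 7.1.1 so that it counts subjects with at least one treatment-related adverse event of grade 4 or higher.

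Keeping 20 costs one number and one column heading per document. Choosing 10 costs six added rows and one recomputed table per document, plus the heading.
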